7.4 PARTICIPANT DISCONTINUATION

Participant discontinuation from study procedures prior to completion of the last study visit may occur for any of the following reasons:

• Dropout (defined as discontinuation initiated by a participant): Participation in the study is strictly voluntary. Participants have the right to withdraw their consent from study participation at any time and for any reason, without penalty. The participant may also initiate discontinuation due to an adverse event.

CONFIDENTIAL Page 49 of 94

- Investigator-initiated: The study investigator may, at their discretion, discontinue a
 participant from the study if they consider it to be in the participant's best interest to do
 so (e.g., for safety concerns), or if the participant does not comply with the study
 requirements.
- Lost to follow-up: For participants who fail to attend scheduled visits, study staff are to
 make at least three attempts to contact the participant prior to considering the
 participant as lost to follow-up. These attempts should be recorded in the source
 documents.
- Sponsor-initiated: For example, if the sponsor is obliged to end the study for administrative or any other reasons.
- Ineligibility (either arising during the study or retrospectively, having been overlooked at screening).

Participants who discontinue prior to administration of the vaccine will be replaced, whereas those withdrawn after administration of the vaccine will not be replaced.

The reason for and date of participant discontinuation will be documented in the source documents and relevant electronic Case Report Form (eCRF). Before entering any category as the reason for the participant's discontinuation from the study, the investigator should make every effort to investigate whether an AE may have been related to the participant's discontinuation from the study. If an AE has been associated with the discontinuation, this must be described on the discontinuation eCRF page, even if it is not the primary reason for the participant's withdrawal. For participants considered lost to follow-up, the discontinuation date for the participant to be captured on the discontinuation eCRF page is the date of the participant's last completed study visit.

In the event of participant discontinuation from the study, reasonable efforts should be made to conduct the following procedures (unless participant consent to do so has been withdrawn):

- Update any AE/SAEs that remained ongoing at the time of the participant's last visit prior to discontinuation.
- If within the protocol defined reporting period, collect any new AE/SAEs and concomitant medications since the participant's last visit and the time of discontinuation.
- Update participant contact information.

CONFIDENTIAL Page 50 of 94

The sponsor or the investigator (following consultation with the sponsor) has the right to discontinue this study at any time. The study may be discontinued at one site or across multiple sites. If the clinical study is prematurely terminated at any of the site, the investigator of the respective site is to promptly inform the study participants and respective IEC and should assure appropriate therapy and follow up for the participants. All procedures and requirements pertaining to the archiving of study documents should be followed. All other study materials (study medication/vaccines, etc.) must be returned to the sponsor.

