7.6.2 Concomitant Medications and Vaccines

At each study visit, the investigator/designee will ask the participants about any prescription or over-the-counter medication(s) taken since the last visit. Any medications taken at any time during the study period must be recorded on source documents and the eCRF with trade and/or generic name, indication, dose, start and end dates until Day 29. Beyond Day 29, only medications taken for SAE / AESI will be recorded.

Any treatments and/or medications specifically contraindicated, e.g., any investigational or non-registered product, any immunosuppressant and immune-modifying drug including systemic steroids, any immunoglobulin and blood product should be checked at each study visit subsequent to the study vaccination. If any become applicable during the study, it will not

CONFIDENTIAL Page 51 of 94

require withdrawal of the participant from the study but may determine a participant's evaluability in the per-protocol analysis.

Any vaccine not foreseen in the study protocol in the period starting at Visit 1 (Day 1) and ending at end of study visit must be recorded in the eCRF.

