9.5 REPORTING PERIOD AND PARAMETER

Solicited AEs will be collected through 7 days following study vaccination using participant diary card. Solicited AEs with onset during the seven-day solicitation period that continue

CONFIDENTIAL Page 54 of 94

beyond the seven-day period will be reported as solicited AEs. Solicited AEs with onset after the seven-day solicitation period will be reported as unsolicited AEs.

Unsolicited AEs will be collected through 28 days (Day 29) following administration of study vaccine. SAEs and AESIs including PIMMCs and AESIs relevant to COVID-19 including possible vaccine-enhanced disease will be collected following administration of the study vaccine until completion of the Day 181 study visit.

Any untoward medical occurrence in a participant prior to administration of the vaccine but after signing the informed consent form, which is assessed by the investigator as being related to a study procedure, must also be documented and reported to the Sponsor.

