10.5.4 Safety Population

All participants who receive the study vaccine [COVOVAX or Control Vaccine (COVISHIELD or COVAXIN)]. All safety analyses will be performed using this population. Participants in the safety population will be analyzed as 'treated' (i.e. actual vaccine received).

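### Section 7.4 lets a vaccinated participant be taken out of follow-up for ineligibility or non-compliance alone, and no SAE/AESI contact or serum sample is then required

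*Protocol*

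**What the plan says.** Section 7.4 concerns leaving the study's visits and procedures, not only its treatment: "Participant discontinuation from study procedures prior to completion of the last study visit may occur for any of the following reasons". The reasons include "Ineligibility (either arising during the study or retrospectively, having been overlooked at screening". The investigator may also discontinue someone for safety, "or if the participant does not comply with the study" requirements. The section separates vaccinated from unvaccinated participants only for replacement: "those withdrawn after administration of the vaccine will not be replaced".

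After discontinuation, reasonable efforts are to be made to update ongoing events, to "collect any new AE/SAEs and concomitant medications since the participant's last visit and the time of discontinuation", and to update contact details. No exit blood sample and no later safety contact is mentioned.

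Other sections bear on this:

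- Sections 4 and 6.1: a single dose on Day 1.
- Section 9.5: SAEs and AESIs "will be collected following administration of the study vaccine until completion of the Day 181 study visit".
- Section 10.5.3: Full Analysis membership needs vaccination and at least one evaluable post-vaccination serum sample.
- Section 10.5.4: the Safety population is "All participants who receive the study vaccine".
- Section 7.6.2: use of a contraindicated product during the study will not "require withdrawal of the participant from the study but may determine a participant's evaluability in the per-protocol analysis".
- Section 7.5: a participant who becomes pregnant is encouraged to complete the remaining visits, unless medically contraindicated.

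**The concern.** In a trial with repeated dosing, finding that a participant is ineligible can be a reason to stop dosing. Here nothing is left to stop after Day 1. Taking a vaccinated participant out of procedures on that ground, or for non-compliance, removes only the observation of someone already exposed.

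Three things are at stake:

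- The SAE/AESI endpoint is defined over the whole study. For a removed participant, new events between removal and Day 181 have no planned route of capture.
- Titres after removal are lost. If removal comes before the first post-vaccination sample (Day 29), the participant is outside the Full Analysis population, which supplies the supplementary check on the Per Protocol GMR analysis (section 10.6.3).
- Sites may differ. Starting an immunosuppressant or becoming pregnant can be read as ineligibility arising during the study, because both appear among the exclusion criteria. Sections 7.6.2 and 7.5 favour keeping such participants, while 7.4 lets them go. Two sites could treat the same case differently and both comply.

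An analysis plan cannot recover data that were never collected, so the place to settle this is the protocol.

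**Working it through.** **Step 1: what is kept and what is lost, by time of removal (vaccinated participant).**

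- Before Day 29: remains in the Safety population with events up to removal. No post-vaccination sample, so not in Full Analysis and not in Per Protocol. All later SAE/AESI capture is lost.
- Between Day 29 and Day 181: remains in Safety and Full Analysis with the data already collected. Later samples and new SAEs/AESIs are lost.
- In both cases, sections 9.9 and 9.11 still ask for known AEs and SAEs to be followed to resolution or stability. New events after removal are not covered.

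**Step 2: the plan's own figures (section 10.4).** Inputs: 186 randomized per cohort, 15% non-evaluable, CV 1.1, GMR margin 0.67 at a true ratio of 1.00, control proportion 95% with true difference 0, margin -10%, one-sided alpha 0.025.

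- Evaluable: 186 × 0.85 = 158.1, so 158, or 79 per arm.
- GMR: log SD = √ln(1 + 1.1²) = 0.8905; margin = -ln 0.67 = 0.4005; noncentrality = 0.4005 / (0.8905 × √(2/79)) = 2.83. Noncentral t power is 80.2%, against 80% stated.
- Proportions: Φ(0.10 / √(2 × 0.95 × 0.05 / 79) - 1.96) = 82.2%, against 82% stated.

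Both reproduce and are not in dispute.

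**Step 3: power if removals before Day 29 come on top of the 15%.** The protocol gives no rate, so the extra share x is an assumption. Evaluable n per arm = 93 × (1 - 0.15 - x).

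- x = 1%: n = 78.1; GMR power 79.8%, proportion power 81.8%
- x = 2%: n = 77.2; 79.3%, 81.3%
- x = 3%: n = 76.3; 78.8%, 80.9%
- x = 5%: n = 74.4; 77.8%, 79.9%

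Per extra 1%, that is about (80.2 - 77.8)/5 = 0.48 points for the GMR and (82.2 - 79.9)/5 = 0.46 for the proportions. If the removals fall inside the 15% allowance, n stays at 79 and power does not change.

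**Step 4: SAE/AESI person-time lost.** Share lost = x × (180 - d)/180, with d the days observed. Again x is assumed.

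- Stopping at the Day 29 visit (d = 28): 0.01 × 152/180 = 0.8%, up to 0.05 × 152/180 = 4.2%
- Stopping at the Day 91 visit (d = 90): 0.5% to 2.5%

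Shares of 1% to 5% are about 2 to 9 people per cohort of 186.

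**Step 5: could a few removals turn a co-primary result?** The Miettinen-Nurminen score statistic is z = (difference + 0.10) / √V, with V from the estimates constrained to a difference of -10% and multiplied by N/(N - 1). The illustrative result is 74/79 for COVOVAX against 75/79 for control; the limit to pass is 1.96.

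- 74/79 against 75/79: z = 2.03, passes
- A responder becomes a non-responder, 73/79: z = 1.71, fails
- One COVOVAX responder is removed, 73/78: z = 2.00, passes
- Two are removed, 72/77: z = 1.964, just passes
- Three are removed, 71/76: z = 1.93, fails

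Removal takes a person out of numerator and denominator alike, so the relevant lines are the last three. Reversal would need three removals, all responders, all in the COVOVAX arm, from a result already near the limit.

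**The case against.** The strongest reply is that section 7.4 only permits these removals. It says they may occur and leaves non-compliance to the investigator. Reasons and dates must be recorded, and a possible link to an adverse event must be looked into. Participants and endpoint assessors are blinded (section 7.2), so there is no evident route by which removal would depend on arm. The 15% allowance may absorb the loss. All of this stands, and it limits the point to avoidable loss of data.

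Four stronger readings are tempting, and the protocol does not support them:

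- A reader might infer that 7.4 and 7.6.2 contradict each other. One allows removal and the other does not require it, for partly different events. That is a difference of approach which leaves the choice open, not opposite rules.
- A reader might infer that the sponsor may remove individuals at will. The only sponsor-initiated example is the sponsor being obliged to end the study.
- A reader might infer that removed participants drop out of the Safety population. They do not: everyone vaccinated stays in it, and anyone with a post-vaccination sample stays in Full Analysis.
- A reader might infer that nothing is gained by removal because the Per Protocol review already deals with such cases. Section 10.5.5 defines a major deviation only as use of an immunosuppressant, an immune-modulating medication or an interfering vaccine, and separately excludes data after infection. Ineligibility overlooked at screening, such as earlier confirmed COVID-19, is not covered. Keeping these participants without amending 10.5.5 would leave them in the primary analysis.

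**Conclusion.** The point holds as a gap in follow-up. For vaccinated participants, section 7.4 allows observation to end for reasons that concern neither consent nor safety, and it sits badly with the Day 181 safety collection in 9.5 and with the retention approach of 7.5 and 7.6.2.

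Its size is modest and rests on an assumed rate of removal. At 1% to 5%, the loss is 0.8% to 4.2% of SAE/AESI person-time if participants stop at Day 29, and about 0.4 to 0.5 points of power per 1% lost before Day 29 beyond the planned allowance.

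A reader might also infer that one lost responder could decide the trial. The calculation does not show this: removing one or two COVOVAX responders from the illustrative result still passes, and nothing in the protocol makes a one-sided run of three likely. This is a cheap improvement in completeness, not a threat to the co-primary conclusions.

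**What to change.** Two changes belong together:

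- **Section 7.4:** state that after vaccination, ineligibility (found later or arising) or non-compliance alone does not end scheduled visits, serum sampling or SAE/AESI collection to Day 181, unless consent is withdrawn or the investigator has a safety reason. The existing participant-initiated and safety grounds stay as they are.
- **Section 10.5.5:** extend the Per Protocol definition so that eligibility violations, and non-compliance that affects immunogenicity, are judged in the blinded review before unblinding.

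The first change without the second would bring ineligible participants into the primary analysis by default. Both concern data collection and analysis sets only.

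The cost is a small amendment in two sections and the completion of a few visits that are already planned.

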7.5 MANAGEMENT OF PREGNANCY DURING STUDY

If a female participant becomes pregnant following administration of vaccine, she will be encouraged to complete remaining visits and study procedures unless medically contraindicated, and if possible and agreed to by the participant, she will continue to be followed for pregnancy outcome. The pregnancy and its outcome will be documented, even if birth occurs after the scheduled end of the study for the participant.

7.6 PRIOR AND CONCOMITANT THERAPY

7.6.1 Prior Medications and Vaccines

Any medications (including vaccines) that were administered to the participant within 30 days prior to the study vaccination will be considered as prior medications for this study. These will be recorded in the eCRF.

7.6.2 Concomitant Medications and Vaccines

At each study visit, the investigator/designee will ask the participants about any prescription or over-the-counter medication(s) taken since the last visit. Any medications taken at any time during the study period must be recorded on source documents and the eCRF with trade and/or generic name, indication, dose, start and end dates until Day 29. Beyond Day 29, only medications taken for SAE / AESI will be recorded.

Any treatments and/or medications specifically contraindicated, e.g., any investigational or non-registered product, any immunosuppressant and immune-modifying drug including systemic steroids, any immunoglobulin and blood product should be checked at each study visit subsequent to the study vaccination. If any become applicable during the study, it will not

CONFIDENTIAL Page 51 of 94

require withdrawal of the participant from the study but may determine a participant's evaluability in the per-protocol analysis.

Any vaccine not foreseen in the study protocol in the period starting at Visit 1 (Day 1) and ending at end of study visit must be recorded in the eCRF.

8. ASSESSMENTS OF IMMUNOGENICITY AND DISEASE INCIDENCE

8.1 IMMUNOGENICITY:

Immunogenicity will be assessed by anti-spike (S) protein IgG antibodies to SARS-CoV-2-Spike antigen by electrochemiluminescence (ECL) using MSD or any other appropriate assay and neutralizing antibodies by using microneutralization (MN) assay.

Immunogenicity testing will be performed in compliance with GCP and GCLP requirements at the following laboratories:

- Anti-S IgG antibodies testing at Christian Medical College, Vellore, India
- Neutralizing antibodies testing at 360biolabs, Burnet Institute, Melbourne, Australia.
- Cell mediated immune (CMI) response assays at NARI-ICMR, Pune, India

Any other laboratories as appropriate may be used, if required.

8.2 INCIDENCE OF COVID-19:

If the participant presents with qualifying symptoms of suspected COVID-19 disease [Appendix II, Table 1] OR history of contact with a confirmed COVID-19 positive case then a swab from nose and/or throat will be collected for RT-PCR testing for SARS-CoV-2 infection. These samples will be processed for SARS CoV-2 RT-PCR testing at respective study sites. Severe COVID-19 disease will be defined as per criteria described in Appendix II, Table 2. Detailed clinical parameters will be collected from medical records. These are likely to include, but are not limited to, oxygen saturation, need for oxygen therapy, respiratory rate and other vital signs, need for ventilatory support, X-ray and CT scan imaging and blood test results, amongst other clinically relevant parameters.

8.3 METHODS FOR PROCESSING, LABEL AND STORAGE OF BLOOD SAMPLES

Approximately 10 mL of blood will be drawn On Day 1, Day 29, Day 91 and Day 181 for anti-S IgG and neutralizing antibody assessments. Additionally, up to 20 ml blood sample may be

CONFIDENTIAL Page 52 of 94

collected from subset of 36 participants (18 from each of the two prime cohorts) for assessment of CMI responses on Day 1, Day 29 and Day 181.

The blood will be processed and sera / CMI samples will be aliquoted according to the Laboratory Manual. All aliquots for anti-S IgG and neutralizing antibodies will be stored at a temperature of -20°C or below. CMI samples will be stored at -70°C or below or in Liquid nitrogen as applicable. Each aliquot (Cryotube / cryovial) will be labeled with the labels provided by Sponsor/designee. All samples will be sent to the Sponsor or Sponsor designated laboratory.

Complete instructions for labeling and storage of samples will be provided in the Laboratory Manual.

9. ASSESSMENT OF SAFETY

9.1 SAFETY MONITORING

The Investigators at each study site will be responsible for continuous close safety monitoring of all study participants, and for alerting the protocol team if concerns arise. An internal team - the Protocol Safety Review (PSRT) will be set up for safety monitoring of the trial participants.

9.2 PROTOCOL SAFETY REVIEW TEAM (PSRT)

Safety will be monitored during the study by on-site clinical staff and routinely by the PSRT, an internal group of physicians which includes the SIIPL Medical Officers, a biostatistician and designated pharmacovigilance medical officer from the CRO. The PSRT may seek independent expert medical opinion as dictated by the occurrence of certain events. There will be periodic reviews of accruing safety data by the PSRT.

9.3 ADVERSE EVENT (AE)

An AE is any untoward medical occurrence in a participant after administration of the vaccine and that does not necessarily have a causal relationship with the vaccine. An AE can therefore be any unfavorable or unintended sign (including an abnormal laboratory finding), symptom, or disease temporally associated with the use of the vaccine, whether or not related to the vaccine. This definition includes exacerbations of pre-existing conditions. Stable pre-existing conditions which do not change in nature or severity during the study are not considered AEs; however, these should be reported as part of the medical history at screening.

CONFIDENTIAL Page 53 of 94

Adverse events that may be related to the study vaccine are listed in the prescribing information for each product.

Solicited AEs are pre-specified local and systemic AEs that occur relatively more frequently or are known to be associated with immunization, which are monitored actively as potential indicators of vaccine reactogenicity. Investigators will not be required to assess causality of solicited AEs if the onset is during the solicitation period.

The following specific solicited adverse events will be monitored for this study:

- Local reactions at injection site: Pain, tenderness, erythema, swelling, and induration
- Systemic reactions: Fever, headache, fatigue, malaise, arthralgia, myalgia, nausea and vomiting

Unsolicited AEs are any AEs reported spontaneously by the participant, observed by the study staff during study visits or those identified during review of medical records or source documents. Solicited AEs with an onset after the seven-day solicitation period will be considered unsolicited AEs.

9.4 SERIOUS ADVERSE EVENT (SAE)

An SAE is any AE that results in any of the following outcomes:

- Death
- Is life-threatening (i.e., the participant was, in the opinion of the investigator, at risk of death at the time of the event; it does not refer to an event which hypothetically might have caused death if it were more severe)
- Requires inpatient hospitalization or prolongation of existing hospitalization
- Results in persistent or significant incapacity or substantial disruption of the ability to conduct normal life functions
- Congenital anomaly or birth defect
- Important medical event that may not result in one of the above outcomes but may jeopardize the health of the study participant or may require medical or surgical intervention to prevent one of the outcomes listed above

9.5 REPORTING PERIOD AND PARAMETER

Solicited AEs will be collected through 7 days following study vaccination using participant diary card. Solicited AEs with onset during the seven-day solicitation period that continue

CONFIDENTIAL Page 54 of 94

beyond the seven-day period will be reported as solicited AEs. Solicited AEs with onset after the seven-day solicitation period will be reported as unsolicited AEs.

Unsolicited AEs will be collected through 28 days (Day 29) following administration of study vaccine. SAEs and AESIs including PIMMCs and AESIs relevant to COVID-19 including possible vaccine-enhanced disease will be collected following administration of the study vaccine until completion of the Day 181 study visit.

Any untoward medical occurrence in a participant prior to administration of the vaccine but after signing the informed consent form, which is assessed by the investigator as being related to a study procedure, must also be documented and reported to the Sponsor.

